The study subjects are mechanically ventilated, critically ill infants and children with acute respiratory failure and as such are known to have mortality rates of 8-22%. We do not anticipate any serious adverse events specifically related to the short-term use of study PN formulations, performance of the metabolic cart, or to blood and urine sampling, but will report standard adverse events. All serious, unexpected, or unanticipated problems that are potentially related to study procedures will be reported to the PI, local IRB, the medical monitor, the DSMB and study sponsor within 24 hours. SAE's and AE's will be reported up to and including 14 days after study enrollment. Ongoing SAE's and AE's will be followed until resolved. A 28-day AE, SAE follow up form will be included in subject monitoring for 28-day vital status. The medical monitor will determine if the serious adverse event is potentially related to study procedures.

For safety monitoring, all adverse and serious adverse events are to be recorded and tracked. In addition to local site reporting for adverse events and serious adverse events, following guidelines are to be followed for this study.

Serious Adverse Event is any of the events listed below:

1. Death within 28 days of enrollment
2. Cardiopulmonary arrest
3. Operation or re-operation
4. Any other event that is not listed in the Expected Adverse Events, that increased risk and/or harm to the patient, may increase hospital length of stay, or require treatment.

If one of these events occurs, the medical monitor and PI within 24 hours of knowledge of the event. These events are also recorded on the SUPPER Adverse Event Log. A chart review of events leading up to the SAE will be required to determine relatedness to the study.

Expected Adverse Events

1. Aspiration of tube feeding
2. Unplanned extubation or need for reintubation
3. Pneumothorax
4. Desaturation < 85%
5. Pulmonary embolus
6. Catheter associated thrombosis
7. Healthcare acquired infections (Catheter associated blood stream infection, ventilator associated pneumonia, catheter associated urinary tract infection) as defined by the hospital infection prevention
8. Readmission to the pediatric intensive care unit
9. Cholestatic jaundice
10. Hyperglycemia (blood glucose >250 mg/dL)
11. Hypoglycemia (blood glucose <60 mg/dL)
12. Hyperammonemia
13. Acute Kidney Failure

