If an adverse event occurs, it is to be noted on the SUPPER Adverse Event Log and the SUPPER Daily Data Collection form for the day the event occurred. All adverse events will be reviewed weekly by [name] to ensure study patient safety.

Report A/E and SAE per local IRB regulations as needed and required.

Data and Safety Monitoring Plan

Should study subjects have adverse events related to study interventions in Aim 1 or Aim 2 we will report these to the local and primary IRB and the Safety Officer ([name]). The DCMC study coordinator will produce Administrative Reports quarterly to describe study progress to include: accrual, subject demographics, and subject status. Reports will also describe adherence to inclusion/exclusion criteria, and protocol deviations. Safety reports will also be generated quarterly, or if enrollment exceeds expectations, at least with every 10 patients enrolled, list frequencies of adverse events, serious adverse events, safety outcomes, deaths, and disease or treatment specific events in blinded groups for review. These reports will be reviewed internally for ongoing quality control and then presented to the Safety Officer, DSMB, and IRB. The Safety Officer will review these quarterly reports to ensure good clinical care and identify any potential trends. The Safety Officer may request interim reports and analysis between meetings or prior to the scheduled interim analysis when necessary. Clinicians will be blinded to the safety monitoring data, as exposure to emerging trends may influence enrollment and care, biasing the study. This is designed as a single-blinded study so that the treating physician and investigative team are aware of group assignment in the event of electrolyte abnormalities, loss of central venous access, and related to feasibility of blinding PN. Our safety officer will also review charts for randomized subjects to ensure that no adverse events are attributable to the study intervention, this is in addition to review by the study PI.

Interim Safety Analysis

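### SAE item 4 has no seriousness threshold, so minor treated events that are not on the expected list count as serious and may dilute or distort the by-group SAE frequencies

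*Combined protocol and SAP*

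**What the plan says.** In the section on serious, unexpected and expected adverse events, the definition opens with "Serious Adverse Event is any of the events listed below", so meeting any one of four items is enough. Items 1 to 3 are death within 28 days, cardiopulmonary arrest, and operation or re-operation. Item 4 is a catch-all for whatever the expected list leaves out, provided it is something "that increased risk and/or harm to the patient, may increase hospital length of stay, or require treatment". Thirteen expected events follow. They include desaturation, high and low glucose, reintubation, healthcare acquired infection, pneumothorax, pulmonary embolus and acute kidney failure. Electrolyte disturbance is not among them.

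An SAE involves the medical monitor and PI within 24 hours, and "A chart review of events leading up to the SAE will be required to determine relatedness to the study". The reporting window is set by "SAE's and AE's will be reported up to and including 14 days after study enrollment".

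The Data and Safety Monitoring Plan has SAE frequencies listed in blinded groups, next to adverse events, safety outcomes and deaths, for the Safety Officer, DSMB and IRB. It does not say whether events or children are counted. It explains the single-blind design by saying that the treating physician and investigators "are aware of group assignment in the event of electrolyte abnormalities, loss of central venous access".

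**The concern.** Item 4 separates serious from non-serious by whether an event was treated or might lengthen the stay, not by how grave it was. In ventilated, critically ill children, being treated says little about gravity. One electrolyte replacement meets the definition.

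Two things are at stake. First, a by-group SAE frequency that mixes minor treated events with grave ones is a weaker signal. A common background in both arms dilutes a real difference. A background that differs by arm can suggest a difference that is not one of serious harm. The second is plausible here, because the manual itself mentions electrolyte abnormalities when it explains why PN is not blinded. Second, the 24-hour step and the chart review are spent partly on events that do not need them.

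**Working it through.** The plan states no SAE rate and no power for safety comparisons, so there is no figure to reproduce. The check has a textual part and an illustration.

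**Text.** Item 4 has three alternatives joined by a final *or*: increased risk or harm, possible lengthening of stay, and need for treatment. The only filter is absence from the expected list. Electrolyte abnormality is foreseen in the monitoring plan and absent from the list, so a treated case qualifies. A pulmonary embolus is on the list, so it cannot qualify under item 4 however severe it is, although it could under items 1 to 3. One sentence is thus both over-inclusive and under-inclusive.

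**Inputs from the documents**
- Window: 14 days for reporting. Study nutrition lasts 168 hours, 168/24 = 7 days, used as a shorter exposure.
- Sample: 40 in total (Statistical Analysis Plan, Aim 2).
- Significance level: 0.05 (stated for Aim 1).
- Only background rate given: mortality of 8-22%.

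**Assumptions**
- 20 per arm; a two-sided Fisher test at 0.05 applied to safety.
- Counting unit: children with at least one SAE.
- Truly serious events in p = 10% v 50%.
- Unlisted treated events at a constant rate q per child-day, equal in both arms and independent of serious events.

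**Formulas**
- Children with at least one unlisted treated event over d days: b = 1 − (1 − q)^d.
- Children with any event classed as an SAE: 1 − (1 − b)(1 − p).
- The observed difference therefore shrinks to (1 − b) × (50% − 10%).
- Power: exact enumeration of Fisher's test over all outcomes at 20 v 20.

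Example, q = 2%, d = 14: b = 1 − 0.98^14 = 24.6%. The arms become 1 − 0.754 × 0.90 = 32% and 1 − 0.754 × 0.50 = 62%, a difference of 30 points instead of 40.

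| q per child-day | b, 14 days | Any SAE, 14 days | Power | b, 7 days | Any SAE, 7 days | Power |
|---|---|---|---|---|---|---|
| 0 | 0% | 10% v 50% | 74% | 0% | 10% v 50% | 74% |
| 1% | 13% | 22% v 57% | 51% | 7% | 16% v 53% | 62% |
| 2% | 25% | 32% v 62% | 34% | 13% | 22% v 57% | 51% |
| 5% | 51% | 56% v 76% | 17% | 30% | 37% v 65% | 29% |
| 10% | 77% | 79% v 89% | 6% | 52% | 57% v 76% | 17% |

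**Distortion.** Suppose truly serious events are 10% in both arms, but unlisted treated events run at 2% per day in one and 5% in the other over 14 days. The SAE proportions become 1 − 0.9 × 0.98^14 = 32% and 1 − 0.9 × 0.95^14 = 56%. The gap of 24 points consists wholly of minor events.

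**Ceiling.** For b to reach 95%, q must be about 20% per day for 14 days: 1 − 0.8^14 = 96%.

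**The case against.** The case against is substantial, and much of it stands.

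- A reader might infer that SAE frequencies will sit near their ceiling. The documents do not support that. They give no rate of unlisted treated events; a ceiling needs about 20% per child-day for two weeks; and if frequencies means event counts, there is no ceiling at all.
- A reader might infer that nearly every routine PICU event becomes an SAE. The expected list already removes many common ones from item 4, such as desaturation, glucose disturbance, reintubation and infection.
- A reader might infer that a real excess of serious harm could not be seen. The monitoring plan lists deaths and other safety outcomes separately. The Interim Safety Analysis section names hospital acquired infection, dialysis, ventilation duration and mortality, not the overall SAE rate, as grounds for requesting unblinded data. It also provides for qualitative review, and the Safety Officer reviews charts.
- The illustration tests a comparison that the plan does not prespecify, and it starts from a large effect. With no background at all, 10% v 30% at 20 per arm has only 24% power, so small numbers limit detection whatever item 4 says. The interim look comes after 40 patients and allows for stopping before enrollment is complete, so 20 per arm may not be the final size.
- The wider 24-hour reporting to the IRB, DSMB and sponsor is confined to problems potentially related to study procedures, and the plan openly prefers to err on the conservative side.

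These points limit the consequence, not the defect. The wording still classes minor treated events as serious, and SAE frequencies by group still go to the oversight bodies. The general trigger for extra safety evaluation refers to other safety outcomes without excluding SAEs. Over-capture is conservative for individual reporting but not for comparing groups.

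**Conclusion.** The point holds in a limited form. Item 4 is a stated rule without a seriousness threshold, and as written it puts minor treated events, with electrolyte replacement as the manual's own example, into the by-group SAE listing. The direction of the dilution is certain if children with at least one SAE are counted and the background is similar in both arms. Its size is not known. Under the assumptions above, power of 74% falls to between 51% and 6% over 14 days, or between 62% and 17% over 7 days, for rates of 1% to 10% per child-day. A background that differs by arm could instead create an apparent difference. Neither a ceiling nor blindness to serious harm is established, and the outcomes monitored separately are untouched. The change is worth making because it is cheap and the listing is read by those who oversee safety.

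**What to change.** Rewrite item 4 so that any event, listed as expected or not, is serious when it is fatal, life-threatening, actually prolongs hospitalization, causes persistent or significant disability, or needs intervention to prevent one of these. Delete the alternative that rests on treatment alone, and replace possible lengthening of stay with actual prolongation.

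Do not add electrolyte disturbance to the expected list unless item 4's exclusion of listed events is removed at the same time. Otherwise a severe electrolyte event could no longer qualify under item 4.

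In the Data and Safety Monitoring Plan, state the counting unit: report SAEs by blinded group as children with at least one event and as event counts. Keep other treated events in the adverse event log as non-serious, where the weekly review still covers them.

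The cost is a protocol wording change and reclassification of logged events, which the medical monitor could do. The small downside is that fewer events get 24-hour notice.

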Patients ≥ 8 years of age are to be approached for assent if the patient is extubated, no longer under the influence of sedatives and analgesics, and the patient is actively receiving early or late parenteral nutrition per study. If no assent obtained because the patient is sedated and unable to participate in the assent process, document this on the assent form and keep in patient study file. If the child does not provide assent once able to cooperate with assent, the intervention is discontinued at that point. All data obtained prior to assent will be utilized. File original assent forms with original parental

consent form in the patient study file and document assent on the SUPPER Enrollment form. Make two copies of the assent form, one for the family and one for bedside.

Randomization

Randomization takes place within 48 hours of PICU admission or initiation of mechanical ventilation. Patients are blocked randomized by age and pre-existing acute or chronic malnutrition (based on admission weight for age BMI z score) to either early or late parenteral nutrition (PN) supplementation. There are 9 randomization stratifications (see table below). Randomization cards are pre-generated; random sequence was created using a random generator with atmospheric noise at random.org. BMI z-score is derived from one of two websites. If <2 years of age, use www.emmes.cpm/study/ped/resources/htwtcalc.htm; if ≥2 years of age, use www.stokes.chop.edu/web/zscore/index/php.

	1month to <3 years	3-10 years of age	11-16 years of age
BMI z score < -1 and >-2 (Low)	A1	B1	C1
BMI z score -1 to +1 (Normal)	A2	B2	C2
BMI z score > +1 and < +2 (High)	A3	B3	C3

To randomize a successfully consented patient, use age and BMI z score to determine which randomization block the patient should be in. Choose the first randomization envelope in the pack. The envelope will have a card stating the intervention arm. Record the patient's study ID, patient age, BMI z-score, name of study personnel randomizing, and date/time of randomization on the card, and staple to the SUPPER Screening Form. Document date, time and study intervention randomized on the patient's SUPPER Screening form and SUPPER Enrollment Log.

Once randomized, email the study PI the patient's study ID, age BMI z score, date and time of randomization, and assigned intervention.

Patient Kits and Supplies

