After 40 patients are enrolled, the Safety Officer and biostatistician blinded to group intervention will examine the safety endpoints stratified by TPN group, blinded into group A and group B. By utilizing the REDCap database, we are able to lock the database during this safety evaluation. We will trigger additional safety evaluations (e.g., more frequent or using an independent clinical panel) analysis if mortality rates (or other safety outcomes) in either arm are statistically different based on the previously mentioned safety reports, or statistically different from historical controls. Furthermore, since safety outcomes are not always powered for “statistical significance”, these safety evaluations will also be examined in a more qualitative fashion, with error being on the side of overly conservative (e.g., any possible difference in safety outcomes). If there is any doubt then an independent panel of clinicians will be convened; if this group decides that there is an unacceptable difference in the two treatment arms then Aim 1 data collection will terminate prior to completing enrollment. Specifically, if either treatment group has significantly increased incidence of hospital acquired infections, increased utilization of dialysis, increased duration of mechanical ventilation, or mortality, then the independent panel can ask for unblinded data. If after data are presented data in an unblinded manner, the independent panel believes that safety concerns are unbalanced between the two arms then the study described in Aim 1 will be discontinued. Aim 2 data and sample collection will continue as planned but in patients on usual care for timing of EN and PN.

A DSMB was convened for this study as part of the Data Safety Monitoring Plan:

DSMB responsibilities

The first responsibility of the DSMB will be to approve the final protocol of the clinical study so that the study/studies can begin enrolling patients. In this case, the Super study is ongoing and the DSMB will provide approval for continuing enrollment. After initial review of the study protocol and consent documents, and at periodic intervals during the course of the study, the DSMB responsibilities are to:

- Provide input to assist the investigators in protecting the safety of study participants;
- Provide input to the investigators on major changes to the research protocol, informed consent documents and plans for data and safety monitoring;

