- Provide input to the investigators on the progress of the study, including periodic assessments of the data quality and timeliness, participant recruitment, accrual and retention, participant risk vs benefit, performance of the study sites, and other factors that may affect study outcomes;
- Review areas of concern regarding the performance of individual sites and provide comment to the investigators on actions to be considered regarding sites that perform unsatisfactorily;
- Consider factors external to the study when relevant information becomes available, such as scientific or therapeutic developments that may have an impact on the safety of the participants or the ethics of the study;
- Provide input to the investigators on modification of the study protocol or possible early termination of the study because of attainment of study objectives, safety concerns, low likelihood of showing a benefit of the intervention, or inadequate performance (such as enrollment and retention problems);
- If appropriate, review the interim analysis of efficacy in accordance with stopping rules which are clearly defined in the protocol and have the concurrence of the DSMB;

Statistical Analysis Plan:

Aim 1. We will assess differences between cumulative percent of goal energy and protein by study arm. We will report means and standard deviations as standard descriptive statistics. We will compare means between study arms with the Student's t tests as we expect cumulative percent of goal energy and protein to have normal distributions. Results will be considered significant at $p < 0.05$. Relationships between cumulative energy and protein delivered with clinical characteristics, mid upper arm circumference changes, and weight for age z scores will be reported by Pearson's correlation coefficient.

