Aim 2. We will assess differences between FABP2, claudin 3, citrulline, lactulose/mannitol ratios, and by study arm. Descriptive plots: serum biomarker (y-variable) over time (x-variable) will be fit, with linear and smoothing splines. Plots are qualitative. Splines allow examination of possible nonlinear relationships and can be used to specify nonlinear or change-point models. We utilize one-way repeated measures ANOVA with the intestinal barrier assays as continuously measured outcomes and time (1,2,3,5, and 7 days) as explanatory variables. If the slope of the serum biomarkers is linear, then change in the slope over time will be calculated using a linear mixed effects model with an AR(1) variance-covariance structure. The variance-covariance structure allows for measurements taken closer together to be more similar than those farther apart in time, and adjusts the standard errors for this correlation. If the relationship between the serum biomarker is not linear in time, then change-point or nonlinear mixed effects models will be used. Aim Multivariable regression analysis will evaluate possible effect modification, or mediation, for non-invasive measures of intestinal epithelial barrier function. Effect modifiers are the interactions with PN group; mediators are those variables that could have a potential additive effect with the PN group. Additionally we will assess any potential confounding that might be present by assessing the change in the parameter estimate for the PN group effect. Potential modifiers, mediators, and confounders, include clinical variables, center effects, and severity of illness. We will test associations between measures of intestinal function and clinical variables, severity of illness, as well as dose and route of nutrition. With 40 subjects total, we will be able to include up to 4 possible predictors; therefore, if effect modifiers are warranted, model simplification will be necessary. If the study is stopped early the analysis plan may be modified due to small sample size.

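### The Aim 1 t test ignores the stratification factors, so it is conservative to the extent that age or BMI z score predicts percent of goal delivered

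*Combined protocol and SAP*

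**What the plan says.** The Randomization section states: "Patients are blocked randomized by age and pre-existing acute or chronic malnutrition (based on admission weight for age BMI z score"). It adds: "There are 9 randomization stratifications (see table below"). The table crosses three age bands with three BMI z bands. Age and BMI z score are written on every randomization card. The section gives no reason for choosing these factors, and no block size or allocation ratio.

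The Statistical Analysis Plan sets the Aim 1 question as "We will assess differences between cumulative percent of goal energy and protein by study arm". The method follows: "We will compare means between study arms with the Student's t tests", justified by "as we expect cumulative percent of goal energy and protein to have normal distributions". The threshold is 0.05. Aim 1 also plans Pearson correlations of delivery with clinical characteristics and anthropometry, but those are not adjusted arm comparisons. The multivariable models under Aim 2 concern the intestinal barrier markers and do not name the stratification factors. No Aim 1 arm comparison uses age or BMI z score.

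No Aim 1 sample size, effect size, SD or power is given. The figure of 40 appears in two other places: the Aim 2 text ("With 40 subjects total, we will be able to include up to 4 possible predictors") and the Interim Safety Analysis ("After 40 patients are enrolled, the Safety Officer and biostatistician blinded to group intervention will examine the safety endpoints").

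**The concern.** Blocking within strata forces the arms to be similar in age and BMI z score, so differences between strata contribute little to the arm difference. The pooled t test does not know this. Its standard error comes from the total within-arm variance, which still includes the between-stratum part. If that part is not zero, the reported standard error is larger than the true one, the interval is too wide and the p value too large.

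The stake is efficiency in a small pilot. There is a lesser point too: if 40 is the size, the average is 40/9 = 4.4 children per stratum. Many blocks would stay unfilled, so some chance imbalance in age or BMI z can remain, and the t test cannot correct it.

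**Working it through.** There is no stated Aim 1 power figure to reproduce, so the check asks how much the choice of test matters over a range of assumptions.

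**Inputs from the documents:** Student's t test without covariates and the 0.05 threshold (Statistical Analysis Plan, Aim 1); 9 strata (Randomization).

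**Assumed, because not stated:** 40 children, 20 per arm (40 is given, but not for Aim 1); 1:1 allocation; blocks of 4; two-sided test; no dropout; true difference 0.909 SD, which gives the t test 80% power at 20 per arm; R², the share of outcome variance explained by age and BMI z, from 0 to 0.3.

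**Step 1: standard errors (outcome SD = 1).**
- t test: √(2/20) = 0.316, whatever R² is.
- True value under perfect stratum balance: √((1 − R²) × 2/20). This is 0.300 at R² = 0.1, 0.283 at 0.2 and 0.265 at 0.3.
- Ratio of the two: 1/√(1 − R²) = 1.054, 1.118 and 1.195.

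Unfilled blocks weaken this a little. In simulated trials at R² = 0.2 with equal strata, the t test reported 0.316 against a true sampling standard error of 0.290. The interval is then 0.316/0.290 = 1.09 times as wide as it should be. The model with age and BMI bands had a true standard error of 0.286.

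**Step 2: power with continuous age and BMI z as covariates.** Where two figures are shown, they come from two separate simulations, one of them with 8,000 trials per setting. Monte Carlo error for that one is about √(0.8 × 0.2/8000) = 0.45 points.

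| R² | t test | Adjusted | Change in power |
|---|---|---|---|
| 0 | 80% | 79% | −1 |
| 0.1 | 80–81% | 83% | +2 to 3 |
| 0.2 | 80–82% | 87% | +5 to 7 |
| 0.3 | 81–82% | 90–91% | +9 |

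Type I error of the t test falls from 5.3% at R² = 0 to 2.7% at R² = 0.3. The adjusted model stays at about 5%.

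**Step 3: check with bands in place of continuous terms** (10,000 trials per setting, equal and skewed strata). With 4 dummies, power against the t test is 79% vs 80% at R² = 0, 83% vs 81% at 0.1, 86–87% vs 81% at 0.2, and 91% vs 82–83% at 0.3. The pattern is the same.

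**Step 4: less favourable assumptions** (4-dummy model, 4,000 trials per setting).
- Factors explain 0% in the early arm and 20% in the late arm: 81% vs 81%.
- 0% and 30%: t test 81%, adjusted 82%; type I error of the t test about 4.2%.
- With continuous covariates and an association in the late arm only, the gain is 1 to 3 points.
- True difference 1.2 SD with 20% explained: t test 97%, adjusted 98%. At 1.5 SD both exceed 99%.

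**Step 5: model size.** Aim 2 allows up to 4 predictors with 40 subjects, which fits 40/10 = 4 if a rule of 10 subjects per predictor is assumed. Arm plus two three-level factors needs 1 + 2 + 2 = 5 terms. Arm with all nine cells needs 1 + 8 = 9. Arm plus continuous age and continuous BMI z needs 3.

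**The case against.** The strongest reply is that the loss may be close to nil. The outcome is a percentage of each child's own goal, so body size is already partly removed. In the early arm PN is titrated every 4 hours to hold delivery constant, which leaves age and BMI z little to explain there. The true contrast may also be large, because by design the arms differ in PN for the first 96 hours. In either case adjustment gains little, as Step 4 shows. This stands, and it is why the size has to be given as a range that includes zero.

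It does not show that the link is absent. Protein is targeted per kg, while fluid is capped at 1600 mL per m² per day. Assuming body surface area = √(height × weight/3600), a child of 5 kg and 58 cm has 0.284 m², or about 91 mL/kg/day. One of 50 kg and 160 cm has 1.491 m², or about 48 mL/kg/day. Room to meet a per-kg goal can therefore vary with age, although the documents do not say how often the cap binds.

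A reader might also infer that the sponsor stratified because these factors were expected to drive nutrition outcomes. The Randomization section does not say so. Nor can 40 be taken as the Aim 1 sample size: it is stated for the Aim 2 models and as the time of the safety look, after which Aim 1 enrolment might still be incomplete.

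Finally, this is a pilot and the error is on the cautious side. That bears on how serious the point is, not on whether the wording should change.

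**Conclusion.** The point holds in a conditional form. Design and analysis do not match: allocation uses age and BMI z score, and the Aim 1 comparison uses neither. To the extent that these factors predict percent of goal delivered, which the documents do not quantify, the t test's standard error is too large and power is lost.

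Two stronger readings are tempting and not supported. One is that the trial certainly loses power: if the factors explain nothing, the t test loses nothing and is about 1 point better. The other is that the test is invalid: the estimate is unbiased and the type I error is at or below its nominal level apart from simulation noise, so a significant Aim 1 result would not be in doubt for this reason.

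The trade favours adjustment: about 1 point of power at risk against roughly 2 to 9 gained at 10% to 30% of variance explained, shrinking to 0 to 3 if only the late arm is affected. All of these figures rest on the assumed sample size, allocation ratio, block size, effect and R². It is a worthwhile gain in efficiency, not a flaw that threatens the trial's conclusions.

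**What to change.** In the Statistical Analysis Plan, Aim 1, make the arm comparison a prespecified linear model, fitted separately for energy and for protein: cumulative percent of goal on arm, continuous age and continuous BMI z score. Report the adjusted arm difference with its 95% CI, and keep the t test as a supporting analysis.

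Use continuous covariates, not bands or the nine cells. Three terms stay within the limit of 4 that the plan sets for Aim 2, should it be applied here. They also avoid a gap in the stratification table, which defines no band for a BMI z score at or below −2 or at or above +2, although the Exclusion Criteria do not exclude such children.

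Do not add the two covariates to the Aim 2 models unless this is reconciled with the 4-predictor limit, since arm, age and BMI z would take three of the four places.

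The cost is a change of wording and 2 degrees of freedom; both covariates are already on the randomization cards. Linear terms may miss part of a non-linear age effect, for instance around the change of PN product at 1 year, which would reduce the gain. The change should be made before outcomes are examined by arm, because covariates chosen afterwards would carry little weight.
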